6.1 Extent of Exposure

Study drug administration will be listed.

For Part B, a cumulative dose level will be determined as the total amount of received study drug up to the current time point (loading dose and maintenance dose).

For Part C, Desmopressin administration will be listed additionally.

6.2 Adverse Events and Bleeding Events

Adverse Events (AEs) are documented in the eCRF section “Adverse Events” and Bleeding Events in the eCRF section “Bleedings”. AEs and bleeding events will be analyzed together.

6.2.1 Data Points

The following tables will be generated:

AE and bleeding event overview (e.g. any AE or bleeding event, any severe AE or bleeding event, any related AE or bleeding event, any hemorrhage (MedDRA SMQ), all embolic and thrombotic events (SMQ), Embolic and thrombotic events, arterial (SMQ), Embolic and thrombotic events, vessel type unspecified and mixed arterial and venous (SMQ), Embolic and thrombotic events, venous (SMQ))

-)
- AEs and bleeding events overall and by SOC and PT

- Related AEs and bleeding events overall and by SOC and PT
- Serious AEs and bleeding events overall and by SOC and PT
- Related serious AEs and bleeding events overall and by SOC and PT
- AEs and bleeding events by maximum severity
- Related AEs and bleeding events by maximum severity
- Serious AEs and bleeding events by maximum severity
- Related serious AEs and bleeding events by maximum severity
- AEs and bleeding events leading to permanently study drug discontinuation or leading to withdrawn from study
- Related AEs and bleeding events leading to permanently study drug discontinuation or leading to withdrawn from study
- Major bleeding events overall and by SOC and PT
- Total ISTH bleeding score (frequency table)
- Bleeding Assessment Score by symptom
- Maximum Bleeding Assessment Score
- AEs and bleeding events with missing assessments (will only be listed)

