Treatment Schedule & Route of Administration	
Part A:
 
 • All dose cohorts will receive a single SC dose of BT200 or placebo on Day 0 at Time 0 
Cohorts 8-10 will be initiated only after submission and authorization of a Substantial Amendment to EC and AGES summarizing the results of Cohorts 1-7.
 
Cohorts 16-17 will be initiated only after submission and authorization of a Substantial Amendment to EC and AGES summarizing the results of Cohorts 8-10 of Part A and Cohort 11 of Part D.
 
Part B:
 
 • All dose cohorts will receive a total of 6 SC or IV doses of BT200 or placebo: 
 ◦ Loading dose regimen consisting of equal IV and SC doses on Day 0 at Time 0 ◦ IV dose will be infused over 2 hours ◦ Maintenance doses: 4 SC doses thereafter every 7 days 
Part C:
 
 • All subjects will receive only a single SC dose of BT200 or placebo on Day -4 • All subjects will receive desmopressin by IV infusion over 30 minutes on Day 0 at approximately 96 hours after the single SC dose of BT200 or placebo 
Part D:
 
 • One cohort will receive BT200 or placebo administered as an IV infusion over 24 hours
Investigational Medicinal Product	
Test Product:
 
 • BT200 as a sterile solution for injection 
Comparator (Placebo):
 
 • Sterile saline for injection 
Non-investigational Medicinal Product (NIMP; Challenge Agent):
 
 • Desmopressin (MINIRIN® Injection) as a sterile solution for injection
Primary Endpoint	
Overall safety and tolerability of BT200, assessed in terms of:
 
 • Serious, drug-related adverse events (AEs) • Premature terminations due to drug-related AEs • Patterns of serious or non-serious, drug-related AEs and/or clinically relevant laboratory abnormalities, vital signs, ECGs, or physical findings suggestive of one or more specific target organs for toxicity of BT200 • Clinically evident bleeding assessed using the ISTH Bleeding Score (see Appendix 6)
Secondary Endpoints	
Pharmacokinetic Endpoints:
 
 • Measured concentration of BT200 (and derived PK parameters)

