2.2 Conduct of Analysis

For Part A, B, C and D, a formal interim analysis is not planned. After all subjects have all visits of the respective study part performed, a topline analysis will be performed for Part A and D separately. Tables, Listings and Figures (TLFs) for the topline analysis can be found in Section 7. Topline analyses might be based on cleaned data for which no SDV was performed yet (due to Covid-19 pandemic, see Section 2.16). The final analysis of all study parts will be performed, when all study parts were fully SDVd, cleaned and once all external data are available and reconciled and the database is closed.

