2.9 Handling Missing Data

Generally, missing values will not be imputed and the analysis will be limited to observed values.

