6.2.2 Definitions and Derivations

- AEs and bleeding events are considered as “related” if the causality to study drug is reported as “related” or “possible”.
- Tables showing AEs or bleeding events by causality, subjects will be counted only in the strongest relationship category but events will be counted in each category.
- In tables showing AEs or bleedings events by maximum severity, subjects will be counted only in the highest grading category but events will be counted in each category.
- An AE or bleeding event is considered as “leading to permanently study drug discontinuation” if “study drug permanently discontinued” is ticked for “action taken on study treatment”.
- An AE or bleeding event is considered as “leading to withdrawal from study” if for “Other action taken”, “withdrawn from study” is answered with “yes”.
- Missing assessments contains missing seriousness, severity and/or causality
- The Total ISTH Bleeding Score will be calculated as the sum of bleeding assessment scores (documented in the eCRF) overall symptoms of a subject. If a subject experienced a symptom more than once, the event with the higher bleeding score will be used.
- The SMQ code for Hemorrhage is 20000038 Haemorrhages (SMQ) which consists of SMQ codes 20000039 “Haemorrhage terms (excl laboratory terms)” and 20000040 “Haemorrhage laboratory terms”.
- The SMQ code for arterial embolic and thrombotic events is 20000082 “Embotic and thrombotic events, arterial (SMQ)”.

- The SMQ code for vessel type unspecified and mixed arterial and venous embolic and thrombotic events is 20000083 “Embolic and thrombotic events, vessel type unspecified and mixed arterial and venous (SMQ)”.
- The SMQ code for venous embolic and thrombotic events is 20000084 “Embolic and thrombotic events, venous (SMQ)”.

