14.x.3.1.11	Yes	Related serious AEs and bleeding events by maximum severity (Safety Population)	Incl. 2-sided 95% CIs
14.x.3.1.12	Yes	AEs and bleeding events leading to permanently study drug discontinuation or leading to withdrawn from study by SOC and PT (Safety Population)	
14.x.3.1.13	Yes	Related AEs and bleeding events leading to permanently study drug discontinuation or leading to withdrawn from study by SOC and PT (Safety Population)	
14.x.3.1.14	Yes	Bleeding Events by SOC and PT (Safety population)	Incl. 2-sided 95% CI
14.x.3.1.15	Yes	Major bleeding events overall and by SOC and PT (Safety Population)	
14.x.3.1.16	Yes	Total ISTH Bleeding Score (Safety Population)	
14.x.3.1.17	Yes	Bleeding Assessment Score by Symptom (Safety Population)	
14.x.3.1.18	Yes	Maximum Bleeding Assessment Score (Safety Population)	
Laboratory parameter			
14.x.3.1.19	Yes	Hematology and Coagulation: Absolute values by time point (Safety Population)	
14.x.3.1.20	Yes	Hematology and Coagulation: Absolute change from randomization by time point (Safety Population)	
14.x.3.1.21	Yes	Hematology and Coagulation: Relative change from randomization by time point (Safety Population)	

14.x.3.1.22	Yes	Hematology and Coagulation: Subjects outside normal range by time point (Safety Population)	
14.x.3.1.23	Yes	Clinical Chemistry: Absolute values by time point (Safety Population)	
14.x.3.1.24	Yes	Clinical Chemistry: Absolute change from randomization by time point (Safety Population)	
14.x.3.1.25	Yes	Clinical Chemistry: Relative change from randomization by time point (Safety Population)	
14.x.3.1.26	Yes	Clinical Chemistry: Subjects outside normal range by time point (Safety Population)	
14.x.3.1.27	Yes	Quantitative Urinalysis: Absolute values by time point (Safety Population)	
14.x.3.1.28	Yes	Quantitative Urinalysis: Absolute change from randomization by time point (Safety Population)	
14.x.3.1.29	Yes	Quantitative Urinalysis: Relative change from randomization by time point (Safety Population)	
14.x.3.1.30	Yes	Quantitative Urinalysis: Subjects outside normal range by time point (Safety Population)	
14.x.3.1.31	Yes	Qualitative Urinalysis by time point (Safety Population)	
14.x.3.1.32	Yes	Vital Signs: Absolute values by time point (Safety Population)	
 • systolic blood pressure [mmHg] • diastolic blood pressure [mmHg] • heart rate [beats/min] • body temperature [C] • body weight [kg]

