16.2.x.3.3	Yes	Adverse Events (Part II)	Dose cohort, Subject number, AE Term, Action taken on study treatment, Action taken on desmopressin (only applicable for Part C), Other action taken, Specification other action taken, Outcome, Recovering date, recovering time, Ongoing at final examination
16.2.x.3.4	Yes	Serious Adverse Events (Part I)	See Listing 16.x.3.1
16.2.x.3.5	Yes	Serious Adverse Events (Part II)	See Listing 16.x.3.2
16.2.x.3.6	Yes	Haemorrhage terms (SMQ) (Part I)	See Listing 16.x.3.1
16.2.x.3.7	Yes	Haemorrhage terms (SMQ) (Part II)	See Listing 16.x.3.2
16.2.x.3.8	Yes	Embolic and thrombotic events, arterial (SMQ) (Part I)	See Listing 16.x.3.1
16.2.x.3.9	Yes	Embolic and thrombotic events, arterial (SMQ) (Part II)	See Listing 16.x.3.2
16.2.x.3.10	Yes	Embolic and thrombotic events, vessel type unspecified and mixed arterial and venous (SMQ) (Part I)	See Listing 16.x.3.1
16.2.x.3.11	Yes	Embolic and thrombotic events, vessel type unspecified and mixed arterial and venous (SMQ) (Part II)	See Listing 16.x.3.2
16.2.x.3.12	Yes	Embolic and thrombotic events, venous (SMQ) (Part I)	See Listing 16.x.3.1
16.2.x.3.13	Yes	Embolic and thrombotic events, venous (SMQ) (Part II)	See Listing 16.x.3.2
16.2.x.3.14	No	Adverse Events with missing assessments (Part I)	See Listing 16.x.3.1
16.2.x.3.15	No	Adverse Events with missing assessments (Part II)	See Listing 16.x.3.2
16.2.x.3.16	Yes	Additional Assessments for Bleeding Events	Dose cohort, Subject number, Bleeding event, Bleeding event verbatim, Start date, Start time, Bleeding Assessment Score, ISTH clinical relevant major bleeding, Major bleeding criteria, ISTH clinical relevant non-major bleeding, Non-major bleeding criteria, End date, End time
16.2.x.3.17	Yes	Hematology and Coagulation Values Outside Normal Range	Dose Level, Subject number, Parameter, Visit, Lab performed, Reason not performed, Collection date, Collection time, same as visit/admission/discharge date, Test, Result, Unit, not done, Reason not done, Outside laboratory limits, Lower limit, Upper limit, Clinically relevant
16.2.x.3.18	Yes	Clinical Chemistry Values Outside Normal Range	See Listing 16.x.3.9
16.2.x.3.19	No	Quantitative Urinalysis Values Outside Normal Range	See Listing 16.x.3.9
16.2.x.3.20	No	Abnormal Qualitative Urinalysis Results	Dose level, Subject number, Parameter, Visit, Lab performed, Reason not performed, Collection date, Collection

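### A terminating adverse event with blank causality is left out of the related counts, so premature terminations due to drug-related AEs can be undercounted

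*SAP*

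**What the plan says.** - **Endpoint.** The protocol synopsis and SAP 1.3.1 both list this element of the primary endpoint: "Premature terminations due to drug-related AEs".
- **Definition of related.** SAP 6.2.2: "AEs and bleeding events are considered as “related” if the causality to study drug is reported as “related” or “possible". It does not mention a causality field left empty.
- **Missing data.** SAP 2.9: "Generally, missing values will not be imputed and the analysis will be limited to observed values". No exception is written for adverse events.
- **Missing assessments.** SAP 6.2.2: "Missing assessments contains missing seriousness, severity and/or causality". The entry for these events in SAP 6.2.1 reads "AEs and bleeding events with missing assessments (will only be listed".
- **Where the element is tabulated.** SAP 7.1, Table 14.x.3.1.13: "Related AEs and bleeding events leading to permanently study drug discontinuation or leading to withdrawn from study by SOC and PT (Safety Population". The overview, Table 14.x.3.1.1, has a matching row, and that table carries two-sided 95% confidence intervals. Both tables are marked Yes for the topline.
- **Where the unassessed events are shown.** SAP 7.2, Listing 16.2.x.3.14, "Adverse Events with missing assessments (Part I", and its second part, 16.2.x.3.15. Both are marked No for the topline.
- **Status of the topline.** SAP 2.2 plans it for Parts A and D and adds: "Topline analyses might be based on cleaned data for which no SDV was performed yet".

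**The concern.** The SAP expects that some events may lack a causality assessment, but it gives no rule for counting them. Under the definition in 6.2.2, an empty field has the same effect on the related count as a recorded judgement of unrelated. For a first-in-human study whose primary endpoint is safety, that default is anti-conservative: a gap in the data can lower the count of drug-related terminations and cannot raise it.

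The cohorts are small, so a single event decides whether a cohort shows any related termination at all. In the topline for Parts A and D the tables restricted to related events are produced, while the listings that would point the reader to unassessed events are not.

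**Working it through.** The documents give no figure for this point (no expected number of terminating events and no expected rate of missing causality), so there is nothing of the plan's own to reproduce. The check traces the rules and then sizes one event.

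**Tracing one event.** Take a subject withdrawn because of an adverse event, with the action taken recorded and causality to study drug blank.

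1. It meets the SAP 6.2.2 definition of an event leading to discontinuation or withdrawal, which uses the action fields only. It therefore enters Table 14.x.3.1.12 and the all-cause termination row of Table 14.x.3.1.1.
2. It does not meet the 6.2.2 definition of related, which needs a recorded answer. Under 2.9 the blank is generally not filled in.
3. It is therefore absent from Table 14.x.3.1.13 and from the related-termination row of Table 14.x.3.1.1. No table in SAP 7.1 specifies a category for missing causality.
4. It appears in Listings 16.2.x.3.2 (causality) and 16.2.x.3.3 (action taken), both in the topline. It is singled out only in 16.2.x.3.14 and 16.2.x.3.15, which are not.

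No sentence in the SAP states the exclusion in step 3. It follows from reading 6.2.2 and 2.9 together.

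**Size of one event.** Inputs: 6 BT200 subjects per cohort (SAP 1.2). Assumption: one such event and no other related termination in the cohort. SAP 2.7 identifies the interval method only by an author's name, so the Wilson and Clopper-Pearson intervals are both given as assumptions.

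Wilson limits, with z = 1.96 and z² = 3.8415: [(x + z²/2) ± z·√(x(n − x)/n + z²/4)] / (n + z²).

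- x = 0, n = 6: the lower limit is 0 and the upper limit is z²/(n + z²) = 3.8415/9.8415 = 39.0%.
- x = 1, n = 6: (2.9207 ± 1.96 × √(0.8333 + 0.9604))/9.8415 = 3.0% to 56.4%.

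| BT200 group | Blank left out | Blank counted as related |
|---|---|---|
| One cohort, n = 6 | 0/6 = 0% (Wilson 0 to 39.0; Clopper-Pearson 0 to 45.9) | 1/6 = 16.7% (Wilson 3.0 to 56.4; Clopper-Pearson 0.4 to 64.1) |
| Part B pooled, n = 2 × 6 = 12, final analysis only | 0/12 = 0% (Wilson 0 to 24.2; Clopper-Pearson 0 to 26.5) | 1/12 = 8.3% (Wilson 1.5 to 35.4; Clopper-Pearson 0.2 to 38.5) |

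The intervals bear on the row in Table 14.x.3.1.1. SAP 7.1 specifies none for Table 14.x.3.1.13.

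**The case against.** The strongest reply is that nothing is hidden. Table 14.x.3.1.12 and the all-cause row of the overview are in the topline. So are the full adverse event listings and the study-end listing (16.2.x.1.7), which gives the primary reason for early termination. With six BT200 subjects per cohort, a gap between Tables 14.x.3.1.12 and 14.x.3.1.13 can be traced line by line. The topline is planned on cleaned data, after complete data entry and a blind data review meeting, and the final analysis follows full source verification and reconciliation. Source verification compares entries with source, whereas blanks are mainly a matter for cleaning. The protocol text available for this review is the synopsis and study diagram, so the data-entry checks, which might make causality mandatory, cannot be seen.

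This stands as far as visibility goes, and it makes a blank less likely. It does not supply a counting rule. The endpoint element is defined by drug-relatedness, so the all-cause table does not report it, and a reader would have to notice an empty cell in a listing.

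A reader might also infer more than the documents support:

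- **That listing only removes these events from every table.** The entry in 6.2.1 sits in a list of outputs and most naturally means that this subset gets a listing and no table of its own. The omission from the related counts comes from the definition of related.
- **That early leavers or subjects absent because of Covid-19 are the likeliest to have blanks.** Nothing in the documents shows this. SAP 2.16 records Covid-19 drop-outs under other reasons; without a separate event marked as leading to withdrawal, they do not reach Table 14.x.3.1.13.
- **That missing severity and seriousness should be set to the worst case too.** That would create severe or serious events that nobody reported, and the argument about related terminations does not require it.

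**Conclusion.** The point holds in conditional form. The rules as written leave a terminating event with blank causality out of the related counts, so this primary-endpoint element can be undercounted. The documents do not support saying that it is undercounted: that needs an event which ended dosing or participation, is in truth drug-related, and still has blank causality when the data are cut. How often this will happen cannot be judged from the documents.

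If it happens once in a six-subject BT200 cohort with no other related termination, the reported rate is 0/6 instead of 1/6 (16.7%). If it does not happen, no result changes. The topline part of the point concerns Parts A and D only; the pooled Part B figures apply to the final analysis. The conclusion rests on reading 6.2.2 and 2.9 together and on no overriding rule existing in documents not available here.

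**What to change.** 1. In SAP 6.2.2, state that an event with missing causality to study drug is counted as related in the topline and final tables, with a footnote in each affected table giving the number so assigned.
2. Show missing severity and missing seriousness as a separate missing row in the tables that use those fields, without imputing them.
3. In SAP 7.2, set Listings 16.2.x.3.14 and 16.2.x.3.15 to Yes for the topline.

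SAP 2.5 unblinds Parts A and D after the topline snapshot, so the rule is best fixed before that snapshot.

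The cost is a few sentences in the SAP, a footnote and a missing row in some tables, and two changed flags. No new data are needed. The downside is that related rates may be slightly higher until queries are resolved; the footnote shows by how many events.

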6.2.2 Definitions and Derivations

- AEs and bleeding events are considered as “related” if the causality to study drug is reported as “related” or “possible”.
- Tables showing AEs or bleeding events by causality, subjects will be counted only in the strongest relationship category but events will be counted in each category.
- In tables showing AEs or bleedings events by maximum severity, subjects will be counted only in the highest grading category but events will be counted in each category.
- An AE or bleeding event is considered as “leading to permanently study drug discontinuation” if “study drug permanently discontinued” is ticked for “action taken on study treatment”.
- An AE or bleeding event is considered as “leading to withdrawal from study” if for “Other action taken”, “withdrawn from study” is answered with “yes”.
- Missing assessments contains missing seriousness, severity and/or causality
- The Total ISTH Bleeding Score will be calculated as the sum of bleeding assessment scores (documented in the eCRF) overall symptoms of a subject. If a subject experienced a symptom more than once, the event with the higher bleeding score will be used.
- The SMQ code for Hemorrhage is 20000038 Haemorrhages (SMQ) which consists of SMQ codes 20000039 “Haemorrhage terms (excl laboratory terms)” and 20000040 “Haemorrhage laboratory terms”.
- The SMQ code for arterial embolic and thrombotic events is 20000082 “Embotic and thrombotic events, arterial (SMQ)”.

- The SMQ code for vessel type unspecified and mixed arterial and venous embolic and thrombotic events is 20000083 “Embolic and thrombotic events, vessel type unspecified and mixed arterial and venous (SMQ)”.
- The SMQ code for venous embolic and thrombotic events is 20000084 “Embolic and thrombotic events, venous (SMQ)”.

6.3 Laboratory Parameters

Laboratory data from scheduled visits and early termination visits will be tabulated. Listings will additionally include results from unscheduled visits.

The following parameters will be assessed in the study and will be included in the statistical analysis:

- Hematology
 - Hemoglobin
 - Hematocrit
 - Red blood cells
 - White blood cells
 - Lymphocytes
 - Monocytes
 - Neutrophils
 - Eosinophils
 - Basophils
 - Platelets
 - Reticulocytes
- Coagulation
 - Prothrombin time
- Clinical Chemistry
 - Sodium
 - Potassium
 - Calcium
 - Chloride
 - Aspartate aminotransferase
 - Alanine aminotransferase
 - Alkaline phosphatase
 - Lactate dehydrogenase
 - Gamma-glutamyltransferase
 - Bilirubin
 - C-reactive protein
 - Blood Urea Nitrogen
 - Creatinine

- Glucose
- Urinalysis
 - Specific gravity
 - pH
 - Leukocytes
 - Nitrite
 - Protein
 - Glucose
 - Ketones
 - Urobilinogen
 - Bilirubin
 - Erythrocytes

Quantitative laboratory parameters (i.e., hematology, clinical chemistry, coagulation, pH, Specific Gravity) will be analyzed descriptively:

- Absolute values by parameter and time point (summary statistics)
- Absolute change from randomization by parameter and time point (summary statistics)
- Relative change from randomization by parameter and time point (summary statistics)
- Number of subjects with values above/below normal range by parameter and time point (frequency statistics)

Qualitative urinalysis parameters will be analyzed by tabulation of urinalysis result by parameter and time point (frequency statistics)

One set of data listings will show parameters outside normal range (hematology, coagulation, clinical chemistry, quantitative urinalysis parameters) and abnormal qualitative urinalysis values, respectively.

For every parameter, boxplots showing the absolute values by study day will be provided.

All parameters will be analyzed using the unit registered by study site in the eCRF. No unit conversion will be done.

